9.3 VARIABLES

The following data will be collected from medical records and will be recorded in the electronic case report form (eCRF) by investigators (or designees) during the study period:

- Informed consent (where applicable)
- Demographics: age at start of first-line treatment, gender, ethnicity
- Stage of disease (IIIb or IV) at start of first-line treatment
- Type of mutations at initial diagnosis
- Methodology used for mutation testing
- Sites of metastases at start of treatment
- Body weight and height at start of treatment
- Eastern Cooperative Oncology Group (ECOG) performance score (PS) (if available) at start of treatment
- Date of start and end of first-line treatment
- First-line treatment administered
- Starting dose of EGFR-TKI (first-or second-line)
- Dose modification(s) and date(s) of EGFR-TKI
- ECOG PS (if available) at start of second-line treatment
- Type of mutations at start of second-line treatment
- Methodology (allele-specific, NGS, sequencing) and material (tissue/liquid biopsy) used for mutational testing
- Sites of metastases at start of second-line treatment
- Date of start and end of second-line treatment
- Second-line treatment administered

- Reason for discontinuation of each treatment (e.g. progressive disease (PD), adverse event (AE))
- Best response to first and second-line treatment (as documented)
- Date of death
- Bevacizumab use with TKI (Yes/No)

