- by definition, "Afatinib" will be the first-line treatment; the start date of the line will be the earliest start date of the field [AAD. AAD_start_date], while the stop date of the line will be the greatest stop date of the field [AAD. AAD_stop_date];
- by definition, "Osimertinib" will be the second-line treatment; the start date of the line will be the earliest start date of the field [OAD. OAD_start_date], while the stop date of the line will be the greatest stop date of the field [OAD. OAD_stop_date];
- subsequent lines will be defined according to the data recorded in the following forms SUBSEQUENT LINES DETAILS (if applicable, for patients with Number of NSCLC treatment lines (as defined before) >2), considering the concatenation of fields [SLD. SLD_treat (**), SLD_treat_sp, SLD_radio_YN]. The start date of this line will correspond to the field [SLD. SLD_start_date]. *The same patient could have more than one record: each record corresponds to a distinct line, which shall be ordered by start date.*

(***) in case it is an "EGFR-TKI", the exact therapy will be retrieved from the field "Type of EGFR-TKI" [SLD. SLD_EGFR] of the same record.

Having defined the start and end dates of each line, the **Duration of treatment lines** will be calculated as the difference between the stop date of the line (^) and the start date of the line + 1 day.

(^) or the end of observation date (as defined later), in case the therapy line was not discontinued at the end of observation.

*In particular, for each patient, the sequences of treatments will be defined taking into consideration the start dates of each line (as defined before). This way, it will be possible to calculate also the **ordinal number** of each line.*

EGFR-TKI generation

- "Erlotinib" and "Gefitinib" will be classified as "1st generation EGFR-TKI";
- "Afatinib" will be classified as "2nd generation EGFR-TKI";
- "Osimertinib" will be classified as "3rd generation EGFR-TKI".

EGFR-TKI starting daily dose (mg) (first- and second-line treatment only)

The starting dose will be retrieved from the following fields of the following forms:

- from the AFATINIB ADMINISTRATION DETAILS form (only for the SEQUENCING COHORT), from the field [AAD. AAD_dose] of the record with earliest non-missing start date (recorded in field [AAD. AAD_start_date]);

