- non-deceased patients with unknown information on treatment interruption at end of observation, ie. those with [PI. PI_pt_class] = (“Living patient” OR “Untraceable patient”) and with “Treatment discontinued?” [EAD. EAD_treat_disc] = “UNK” in the latest record of the EGFR-TKI ADMINISTRATION DETAILS form referred to the index EGFR-TKI treatment (as defined before). For these patients, the time to censoring will be computed as the difference between the greatest start date [EAD. EAD_start_date] of the EGFR-TKI ADMINISTRATION DETAILS form referred to the index EGFR-TKI treatment (as defined before) and the start date of the Index EGFR-TKI therapy (as defined before) + 1 day.

Time on treatment for SEQUENCING COHORT

The following patients will be considered as having the event “osimertinib treatment discontinuation after switch from afatinib”:

- patients with discontinuation of osimertinib treatment, ie. those with discontinuation defined as “Treatment discontinued?” [OAD. OAD_treat_disc] = “Yes” in the latest record of the OSIMERTINIB ADMINISTRATION DETAILS form. For these patients, the time to event will be computed as the difference between the field “Stop date with this dose” [OAD. OAD_stop_date] of the above-mentioned record and the start date of the first-line therapy (as defined before) + 1 day;
- deceased patients at time of inclusion in the study, ie. those with [PI. PI_pt_class] = “Deceased patient”. For these patients, the time to event will be computed as the difference between the “Date of death” [PI. PI_date_death] and the start date of the first-line therapy (as defined before) + 1 day.

The same patient could have multiple events, but for the purpose of the analysis only the earliest event will be considered.

Other patients will be considered as censored observations. The following situations might be observed:

- non-deceased patients with evidence of ongoing treatment at end of observation, ie. those with [PI. PI_pt_class] = (“Living patient” OR “Untraceable patient”) and with “Treatment discontinued?” [OAD. OAD_treat_disc] = “No” in the latest record of the OSIMERTINIB ADMINISTRATION DETAILS form. For these patients, the time to censoring will be computed as the difference between the end of observation date (as defined later) and the start date of the first-line therapy (as defined before) + 1 day;

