- for **OS from osimertinib discontinuation**, as the difference between the “Date of death” [PI. PI_date_death] and the Stop date of second-line therapy (as defined before, namely osimertinib) + 1 day. This algorithm will be computed only for patients with osimertinib discontinuation (ie. those with calculated stop date of second-line therapy).

Other patients will be considered as censored observations. The following situations might be observed:

- alive patients at end of observation, ie. those with [PI. PI_pt_class] = “Living patient”. For these patients, the time to censoring will be computed as the difference between the end of observation date (as defined later) and the start date of afatinib / stop date of osimertinib therapy (depending on the type of OS evaluated) + 1 day;
- untraceable patients at end of observation, ie. those with [PI. PI_pt_class] = “Untraceable patient”. For these patients, the time to censoring will be computed as the difference between the latest date when the patient was known to be alive (ie. [PI. PI_date_alive]) and the start date of afatinib / stop date of osimertinib therapy (depending on the type of OS evaluated) + 1 day.

End of observation date

- For alive patients (ie. those with [PI. PI_pt_class] = “Living patient”), it will correspond to the “Date of data collection (dd/mmm/yyyy)” [PI. PI_date_coll]
- For deceased patients (ie. those with [PI. PI_pt_class] = “Deceased patient”) it will correspond to the “Date of death (dd/mmm/yyyy)” [PI. PI_date_death]
- For untraceable patients (ie. those with [PI. PI_pt_class] = “Untraceable patient”) it will correspond to the “Date patient last known to be alive (dd/mmm/yyyy)” [PI. PI_date_alive]

Duration of observation window (in months) starting from the first-line treatment start

- For alive patients (ie. those with [PI. PI_pt_class] = “Living patient”), it will be calculated as the difference between the end of observation date (as defined before) and Start date of first-line therapy (as defined before) + 1 day
- For deceased patients (ie. those with [PI. PI_pt_class] = “Deceased patient”) it will be calculated as the difference between the end of observation date (as defined before) and Start date of first-line therapy (as defined before) + 1 day

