4.2.6 Overall Survival

Table 21-SEQ. Overall Survival from afatinib start (ELIGIBLE PATIENTS of the Sequencing Cohort) - Secondary objective #2

The table will provide the Kaplan-Meier estimates of quartiles of time to death from afatinib start (with their 95% Confidence Intervals, using Greenwood's variance estimate) (see algorithm for Overall Survival in the "Computed variables" chapter).

Moreover, a Kaplan-Meier survival curve will be provided. The analysis will be represented on a plot having the time to event on the horizontal axis and the percentage of event-free patients on the vertical axis.

Table 22-SEQ. Overall Survival from osimertinib discontinuation (ELIGIBLE PATIENTS of the Sequencing Cohort)

[figure not shown]
The table will provide the Kaplan-Meier estimates of quartiles of time to death from osimertinib discontinuation (with their 95% Confidence Intervals, using Greenwood's variance estimate) (see algorithm for Overall Survival in the "Computed variables" chapter).

Moreover, a Kaplan-Meier survival curve will be provided. The analysis will be represented on a plot having the time to event on the horizontal axis and the percentage of event-free patients on the vertical axis.

In this analysis, only patients who discontinued osimertinib (see "Computed variables" chapter) will be considered.

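### OS from osimertinib discontinuation (Table 22-SEQ) selects patients by a dose-level stop date, so as written it can admit living or untraceable patients who changed dose and were never recorded as stopping

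*SAP*

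**What the plan says.** The protocol (9.3 Variables) collects "Dose modification(s) and date(s) of EGFR-TKI", so one patient can have several osimertinib records. SAP section 3 confirms that the stop date belongs to a dose record. For the primary endpoint, "the time to event will be computed as the difference between the field “Stop date with this dose” [OAD. OAD_stop_date"] of the latest record is used.

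SAP section 3 then treats the end of osimertinib in two ways.

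- **Time on treatment for SEQUENCING COHORT (Table 20-SEQ).** A discontinuation needs "OAD. OAD_treat_disc] = “Yes” in the latest record of the OSIMERTINIB ADMINISTRATION DETAILS form". Non-deceased patients whose latest record says No or UNK are censored.
- **Type of NSCLC treatment patterns for SEQUENCING COHORT.** The start of the osimertinib line is its earliest start date, "while the stop date of the line will be the greatest stop date of the field [OAD. OAD_stop_date"]. The discontinuation flag is not mentioned.

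The second definition feeds Overall Survival for SEQUENCING COHORT, in the part on survival from osimertinib discontinuation: "This algorithm will be computed only for patients with osimertinib discontinuation (ie. those with calculated stop date of second-line therapy"). SAP 4.2.6 says of Table 22-SEQ: "In this analysis, only patients who discontinued osimertinib" will be considered, and refers back to the Computed variables chapter.

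**The concern.** A dose change closes one record and opens another. A closed record therefore shows that a dose ended, not that the drug was stopped. Taking the latest closed date as the end of the line, and the existence of that date as proof of discontinuation, turns a dose change into a discontinuation for anyone whose later record is still open.

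Two things are at stake. Table 22-SEQ is meant to describe survival after osimertinib, but would include time spent on osimertinib. And Tables 20-SEQ and 22-SEQ would disagree about which patients discontinued, with nothing in the report to explain the difference.

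**Working it through.** The plan states no figure for this analysis, so there is nothing to reproduce. The check has two parts: apply the written rules to one patient, then bound the effect under stated assumptions.

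**1. One patient (dates and doses invented for illustration).** Living patient. Record 1: 80 mg, 1 Jan 2018 to 30 Jun 2018. Record 2: 40 mg from 1 Jul 2018, no stop date, discontinued = No. Data collection: 30 Jun 2020.

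| Rule in SAP section 3 | Result |
|---|---|
| Line stop date = greatest dose stop date | 30 Jun 2018 |
| Table 20-SEQ: flag in latest record | No, so censored as ongoing |
| Table 22-SEQ: calculated stop date exists? | Yes, so included |
| Table 22-SEQ time = 30 Jun 2020 − 30 Jun 2018 + 1 day | 732 days; 732 / 30.4375 = 24.0 months, censored |

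The same patient without a dose change has no stop date and stays out of Table 22-SEQ. A patient who changes dose and later stops gets the same date under both rules. A non-deceased patient with status UNK in the latest record and an earlier closed record also enters Table 22-SEQ, although Table 20-SEQ censors that patient.

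**2. Does other text repair this?**

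- The footnote to the treatment patterns substitutes "or the end of observation date (as defined later), in case the therapy line was not discontinued at the end of observation", but it is attached to the duration of treatment lines, not to the stop date or to entry into Table 22-SEQ.
- The imputation of a missing treatment stop date by the date of death (opening of section 3) covers deceased patients only.
- Section 6 has the Table 22-SEQ algorithm checked for 20% of patients. A program that follows the written rule would pass.

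**3. Direction.** The wrongly added patients are not deceased, so each contributes censored time and no death. This enlarges the risk set and raises the Kaplan-Meier curve.

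**4. Size, under assumptions.** None of these inputs is in the documents except the cohort size of 200: exponential time on osimertinib with median 12 or 18 months; true median survival after stopping of 10 months; data collection uniform at 10 to 40 months after osimertinib start; dose change uniform at 1 to 9 months; 600 simulated cohorts per cell. True discontinuers number about 147 (12-month median) or 119 (18-month median). Without the error the median is about 10.1 months.

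| Patients with a dose change | Wrongly added | Table 22-SEQ median (months) | Shift from 10.1 |
|---|---|---|---|
| 5% | 3–4 | 10.3–10.8 | 0.2–0.7 |
| 10% | 5–8 | 10.7–11.3 | 0.6–1.2 |
| 20% | 11–16 | 11.3–12.5 | 1.2–2.4 |

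The error-free median itself varies over about 10.0 to 10.2 between cells, so the largest shift is about 12.5 − 10.0 = 2.5 months. The 95% interval for this median is about 5 to 6 months wide under the same assumptions. At 5% to 10% dose change the shift is thus at most about 1.2 / 5 = 24% of its width.

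A wider set of assumptions (30% to 50% still on osimertinib, 5% to 20% of those with an earlier dose change, true median 6 to 15 months) adds 3 to 20 patients and shifts the median by 0.2 to 5.2 months. The size is therefore driven by what is assumed.

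**The case against.** The best defence is that the intent is plain. Both section 3 and section 4.2.6 restrict the analysis to patients who discontinued, and section 3 holds a sound definition of discontinuation for the primary endpoint. A careful programmer could apply it. This shows that the plan does not mean to count dose changes as discontinuations. It does not repair the rule: section 4.2.6 points back to section 3, and the passage there that governs this analysis spells out discontinuation as having a calculated stop date.

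The eCRF is not available, so how an ongoing record is stored cannot be confirmed. That stands as a condition on the dose-change date being time zero.

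A reader might infer that Table 22-SEQ as a whole must be biased upward. The documents do not support that. Patients who died with no recorded osimertinib stop get the date of death as stop date and, with the added day, enter as deaths at day 1, which pulls the other way. Only the direction of this one error is established.

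A reader might also extend the point to afatinib, whose line stop date has the same form. The documents show no discontinuation flag on the afatinib form. Afatinib has ended by the time second-line osimertinib starts, and the rule misfires only if the last afatinib stop date is missing, which is a data-cleaning matter. That extension is not made here.

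**Conclusion.** The written rule is wrong for Table 22-SEQ and inconsistent with Table 20-SEQ. Provided that ongoing dose records carry no stop date, non-deceased patients with a dose change and no recorded discontinuation are entered as discontinued on the dose-change date. By itself this pushes estimated post-osimertinib survival upward. The amount is unknown: about 0.2 to 2.5 months on the median in the main assumed scenarios, small against the interval width at 5% to 10% dose change. It is zero if no such patient had a dose change, or if the programmer applies the Table 20-SEQ flag.

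The reach is limited. It would be wrong to infer that the primary endpoint is affected, because Table 20-SEQ uses the discontinuation flag. Nor is a labelled secondary objective affected: Table 21-SEQ (survival from afatinib start) carries that label and Table 22-SEQ carries none. It is worth correcting because the inconsistency is clear and the remedy is cheap.

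**What to change.** In SAP section 3, Type of NSCLC treatment patterns for SEQUENCING COHORT, set the osimertinib line stop date to OAD_stop_date of the latest osimertinib record, and only when OAD_treat_disc is Yes in that record. Keep the date-of-death imputation for deceased patients as a stated exception, so that the two rules do not conflict.

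Under Overall Survival for SEQUENCING COHORT, replace the test for a calculated stop date by the same flag when selecting non-deceased patients for survival from osimertinib discontinuation. Leave the afatinib rule as it is.

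The cost is two sentences and one programming condition. No new data are needed, since the flag already serves Table 20-SEQ. Table 22-SEQ loses only non-deceased patients who were not recorded as having stopped.

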(*) this means that if the start date of the index EGFR-TKI therapy is 9.49 months before date of data collection, the patient violates this criterion. This tolerance window has been agreed with the Sponsor during the Data Analysis Strategic Meeting, and will not be further discussed. Only in case exact day is not known and this makes the evaluation critical with the respect to the tolerance window, then case-by-case discussion will be done with the Sponsor.

Criterion 8 (UNCOMMON MUTATION COHORT). Patient not treated for EGFR mutated NSCLC within a clinical trial

- “Cohort” [PI. PI_coh_ty] = “Uncommon Mutation cohort” AND
- “1. Patient treated for EGFR mutated NSCLC within a clinical trial” in the ELIGIBILITY CRITERIA form [EC. EC_EC_1_umc] = “No” AND
- “1. Patient treated for EGFR mutated NSCLC within a clinical trial” in the PROTOCOL DEVIATION FORM [PDF. PDF_EC1_umc] is not flagged

Criterion 8 (SEQUENCING COHORT). Patient not treated for EGFR mutated NSCLC within a clinical trial nor participated in GioTag study

- “Cohort” [PI. PI_coh_ty] = “Sequencing cohort” AND
- “1. Patient treated for EGFR mutated NSCLC within a clinical trial or participated in GioTag study” in the ELIGIBILITY CRITERIA form [EC. EC_EC_1_sc] = “No” AND
- “1. Patient treated for EGFR mutated NSCLC within a clinical trial or participated in GioTag study” in the PROTOCOL DEVIATION FORM [PDF. PDF_EC1_sc] is not flagged

Patients treated with osimertinib within an early access program/compassionate use program (EAP/CUP) are allowed.

Criterion 9. Patient without active brain metastases at start of EGFR-TKI therapy (independent of treatment line)

- “2. Patient with active brain metastases at start of EGFR-TKI therapy (independent of treatment line)” in the ELIGIBILITY CRITERIA form [[EC. EC_EC_2](#)] = “No” AND
- “2. Patient with active brain metastases at start of EGFR-TKI therapy (independent of treatment line)” in the PROTOCOL DEVIATION FORM [[PDF. PDF_EC2](#)] is not flagged

Criterion 10 (UNCOMMON MUTATION COHORT only). Patient not treated with osimertinib without further uncommon mutations than acquired T790M

- “Cohort” [[PI. PI_coh_ty](#)] = “Uncommon Mutation cohort” AND
- “3. Patient treated with osimertinib with no further uncommon mutation than acquired T790M” in the ELIGIBILITY CRITERIA form [[EC. EC_EC_3_umc](#)] = “No” AND

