- non-deceased patients with unknown information on treatment interruption at end of observation, ie. those with [PI. PI_pt_class] = (“Living patient” OR “Untraceable patient”) and with “Treatment discontinued?” [OAD. OAD_treat_disc] = “UNK” in the latest record of the OSIMERTINIB ADMINISTRATION DETAILS form. For these patients, the time to censoring will be computed as the difference between the greatest start date [OAD. OAD_start_date] of the OSIMERTINIB ADMINISTRATION DETAILS form and the start date of the first-line therapy (as defined before) + 1 day.

Time to second-line treatment failure for UNCOMMON MUTATIONS COHORT

The algorithm will be computed only for patients with Number of NSCLC treatment lines (as defined previously) >1. The time to event will be computed considering the time elapsed from start of first-line treatment (regardless the type of treatment) to stop of second-line (regardless the type of treatment) or death by any cause.

The following patients will be considered as having the event “treatment discontinuation”:

- patients with discontinuation of second-line treatment, ie. those with non-missing “Stop date of this line” [**Second-line treatment period / TREAT. TREAT_stop_date**]. For these patients, the time to event will be computed as the difference between the stop date of the second-line treatment (as defined before) and the start date of the first-line therapy (as defined before) + 1 day;
- deceased patients at time of inclusion in the study, ie. those with [**PI. PI_pt_class**] = “Deceased patient”. For these patients, the time to event will be computed as the difference between the “Date of death” [**PI. PI_date_death**] and the start date of the first-line therapy (as defined before) + 1 day.

The same patient could have multiple events, but for the purpose of the analysis only the earliest event will be considered.

Other patients will be considered as censored observations. The following situations might be observed:

- non-deceased patients with evidence of ongoing second-line treatment at end of observation, ie. those with [**PI. PI_pt_class**] = (“Living patient” OR “Untraceable patient”) and with “Ongoing at end of observation?” [**Second-line treatment period / TREAT. TREAT_ongoing**] = “Yes”. For these patients, the time to censoring will be computed as the difference between the end of observation date (as defined later) and the start date of the first-line therapy (as defined before) + 1 day;

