4.2.4 NSCLC treatments

Table 15-SEQ. NSCLC treatment patterns (ELIGIBLE PATIENTS of the Sequencing Cohort)

See corresponding table for the UNCOMMON MUTATION COHORT. However, the results will be focused on the 3rd or subsequent lines (if any), since the whole cohort will have in common the initial pattern “afatinib→osimertinib” by definition.

Table 16-SEQ. Details of first-line EGFR-TKI treatment (afatinib) (ELIGIBLE PATIENTS of the Sequencing Cohort)

The table will provide:

- absolute and relative frequency of afatinib starting daily dose (mg) (see “Computed variables” chapter).
- descriptive statistics (mean, standard deviation, quartiles, min, max) of Duration of afatinib treatment (see “Computed variables” chapter).

Descriptives and percentages will be calculated over the number of ELIGIBLE PATIENTS in the cohort.

Table 17-SEQ. Response to first-line treatment (afatinib) (ELIGIBLE PATIENTS of the Sequencing Cohort) – Secondary objective #1

See corresponding table for the UNCOMMON MUTATION COHORT.

Table 18-SEQ. Details of second-line EGFR-TKI treatment (osimertinib) (ELIGIBLE PATIENTS of the Sequencing Cohort)

The table will provide:

- absolute and relative frequency of osimertinib starting daily dose (mg) (see “Computed variables” chapter)
- patients’ distribution (absolute and relative frequency) by “Which programme was used for patient treatment with osimertinib?” [[Second-line treatment period / TREAT.TREAT_osim_progr](#)]
- descriptive statistics (mean, standard deviation, quartiles, min, max) of Duration of osimertinib treatment (see “Computed variables” chapter)

Descriptives and percentages will be calculated over the number of ELIGIBLE PATIENTS in the cohort.

Table 19-SEQ. Response to second-line treatment (osimertinib) (ELIGIBLE PATIENTS of the Sequencing Cohort) – Secondary objective #1

See corresponding table for the UNCOMMON MUTATION COHORT.

Moreover, the table will provide patients’ distribution (absolute and relative frequency) by “Presence of brain metastases at the end of osimertinib treatment line?” [[Second-line treatment period / RESP.RESP_brain_met](#)].

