5.2.4 NSCLC treatments

Table 15-SEQ. NSCLC treatment patterns (ELIGIBLE PATIENTS of the Sequencing Cohort)

See corresponding table for the UNCOMMON MUTATION COHORT. However, the results will be focused on the 3rd or subsequent lines (if any), since the whole cohort will have in common the initial pattern “afatinib→osimertinib” by definition.

Table 16-SEQ. Details of first-line EGFR-TKI treatment (afatinib) (ELIGIBLE PATIENTS of the Sequencing Cohort)

ELIGIBLE PATIENTS (N=xxx)		
Afatinib starting daily dose (mg)	50 mg	xxx (xx.x%)
	40 mg	xxx (xx.x%)
	30 mg	xxx (xx.x%)

Duration of afatinib treatment	N	xxx
	Mean	xx.x
	SD	xx.x
	25th percentile	xx.x
	Median	xx.x
	75th percentile	xx.x
	Min	xx.x
	Max	xx.x

Table 17-SEQ. Response to first-line treatment (afatinib) (ELIGIBLE PATIENTS of the Sequencing Cohort) – Secondary objective #1

See corresponding table for the UNCOMMON MUTATION COHORT.

Table 18-SEQ. Details of second-line EGFR-TKI treatment (osimertinib) (ELIGIBLE PATIENTS of the Sequencing Cohort)

ELIGIBLE PATIENTS (N=xxx)		
Osimertinib starting daily dose (mg)	80 mg	xxx (xx.x%)
	40 mg	xxx (xx.x%)
Programme used for patient treatment	Regular Clinical Practice	xxx (xx.x%)
	Through EAP/CUP	xxx (xx.x%)
Duration of osimertinib treatment	N	xxx
	Mean	xx.x
	SD	xx.x
	25th percentile	xx.x
	Median	xx.x
	75th percentile	xx.x
	Min	xx.x
	Max	xx.x

Table 19-SEQ. Response to second-line treatment (osimertinib) (ELIGIBLE PATIENTS of the Sequencing Cohort) – Secondary objective #1

		ELIGIBLE PATIENTS (N=xxx)
Best response achieved	Complete response (CR)	xxx (xx.x%)
	Partial Response (PR)	xxx (xx.x%)
	Stable Disease (SD) or Non-CR/Non PD	xxx (xx.x%)
	Disease Progression	xxx (xx.x%)
	UNK	xxx (xx.x%)
Overall Response (ORR)		xxx (xx.x%)
Duration of response (in months)	N	xxx
	Mean	xx.x
	SD	xx.x
	25th percentile	xx.x
	Median	xx.x
	75th percentile	xx.x
	Min	xx.x
	Max	xx.x
Presence of brain metastases at the end of osimertinib treatment line?	Yes	xxx (xx.x%)
	No	xxx (xx.x%)
	UNK	xxx (xx.x%)

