5.2.5 Time on treatment

Table 20-SEQ. Time on treatment (ELIGIBLE PATIENTS of the Sequencing Cohort) – Primary objective

Quartiles Estimates			
95% Confidence Interval			
%	Point Estimate	[Inferior	Superior)
75	xx.xx	xx.xx	xx.xx
50	xx.xx	xx.xx	xx.xx
25	xx.xx	xx.xx	xx.xx

Total	Failed	Censored	Percent Censored
xx	xx	xx	xx.xx

A Kaplan-Meier survival curve will be provided.

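### Table 18-SEQ summarises osimertinib duration with plain mean, SD and quartiles while counting ongoing lines as ended at end of observation, so the mean and normally the upper quartile come out too short

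*SAP*

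**What the plan says.** SAP section 3 (treatment patterns for the sequencing cohort) defines the duration of a line as stop date minus start date plus one day. The stop date is replaced by the end of observation date when the line is still running: "or the end of observation date (as defined later), in case the therapy line was not discontinued at the end of observation". For living patients that date is the date of data collection. For untraceable patients it is the "Date patient last known to be alive".

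SAP 4.2.4 specifies for Table 18-SEQ "descriptive statistics (mean, standard deviation, quartiles, min, max) of Duration of osimertinib treatment", calculated over all eligible patients. The layout in SAP 5.2.4 labels the row "Duration of osimertinib treatment" and has lines for N, mean, SD, quartiles, minimum and maximum. It has no line for the number ongoing.

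For the primary endpoint (Table 20-SEQ), section 3 censors the same ongoing patients: "the time to censoring will be computed as the difference between the end of observation date (as defined later", counted from afatinib start. Patients of unknown treatment status are censored at "the greatest start date [OAD. OAD_start_date] of the OSIMERTINIB ADMINISTRATION DETAILS form". The layout in SAP 5.2.5 prints "Percent Censored". Protocol 9.7 likewise censors patients not known to have stopped.

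**The concern.** The report would treat one and the same ongoing osimertinib line as censored in Table 20-SEQ and as complete in Table 18-SEQ. Table 20-SEQ cannot stand in for Table 18-SEQ, because its clock starts at afatinib.

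Osimertinib is the second half of the sequence under study. Although Table 18-SEQ carries no objective label, readers will take its row as the time patients stay on osimertinib. Nothing in the table warns them that some values are truncated.

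The duration rule also does not say how a line of unknown status is handled, whereas the primary endpoint has an explicit rule.

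**Working it through.** **Direction.** Let T be the true osimertinib duration and C the time from osimertinib start to end of observation. The recorded value is Y = min(T, C), so Y ≤ T for every confirmed ongoing line. No mean or quantile of Y can therefore exceed that of T. The upper quartile escapes only if every ongoing line already lies above it.

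**Share ongoing.** The event in Table 20-SEQ is osimertinib discontinuation or death. The patients censored there are therefore those whose osimertinib line is ongoing or of unknown status. Protocol 9.5 tabulates 10%, 20% and 30% censoring. Protocol 7.2 reports 52% maturity for time to treatment failure in the earlier real-world study of this sequence, that is, about 48% censored.

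**Mean, exponential T, independent C.** E[Y] = E[T] × P(T ≤ C), so the mean is short by exactly the share ongoing: 10%, 20% and 30% at the three levels of Protocol 9.5. With a rising hazard (Weibull shape 1.3), it is short by about 7%, 14% and 22%.

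**Assumed inputs.** The plan states no osimertinib-alone figure to reproduce, so these are ranges anchored on its own numbers.
- True median 10 to 16 months. The 10 is the entry threshold that Protocol 9.2.1 takes from a second-line osimertinib trial. Sequence time minus first-line afatinib time gives 27.6 − 13.7 = 13.9 and 30 − 13.7 = 16.3 (Protocol 7.2 and 9.5). This is rough, since medians do not subtract.
- Follow-up uniform from 9.5 months. SAP 2.1, criterion 7 says: "if the start date of the index EGFR-TKI therapy is 9.49 months before date of data collection, the patient violates this criterion". The upper limit is 36 months (availability of 2 to 3 years in most regions, Protocol 9.9) or 60 months (roughly first approval in November 2015 to the end of 2020).

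**Simulation** (2 million patients per row; plain summary of Y / true value, in months):

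| Median, longest follow-up, shape | Ongoing | Mean | SD | Median | Upper quartile |
|---|---|---|---|---|---|
| 10, 60, Weibull 1.3 | 9.8% | 11.4 / 12.2 | 8.2 / 9.5 | 9.9 / 10 | 15.8 / 17.0 |
| 10, 60, exponential | 14.4% | 12.4 / 14.4 | 10.6 / 14.4 | 9.9 / 10 | 17.5 / 20.0 |
| 16, 36, Weibull 1.3 | 36.4% | 14.3 / 19.6 | 8.2 / 15.2 | 13.2 / 16 | 19.6 / 27.3 |
| 16, 36, exponential | 39.4% | 14.0 / 23.1 | 9.0 / 23.1 | 12.9 / 16 | 20.1 / 32.0 |

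Hand check of the last row: true mean 16 / ln 2 = 23.08, and 23.08 × (1 − 0.394) = 13.99.

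With follow-up set to give 10/20/30% ongoing (medians 10 to 16), the upper quartile is short by 7.5–8.2 / 14.1–15.6 / 21.3–23.0% (Weibull) or 8.9–9.7 / 17.0–18.5 / 26.1–27.6% (exponential). The median is short by 1–6 / 2–10 / 2–15% (Weibull).

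**Lower quartile.** Living ongoing patients contribute at least 9.5 months, which is above the true lower quartile in all these scenarios, so they leave it unchanged. Untraceable patients can fall below 9.5 months. If 10% are untraceable, with the last-alive date uniform before data collection, the lower quartile is 4.85 instead of 5.08 (mildest Weibull row) or 7.33 instead of 8.13 (worst Weibull row), about 5% to 10% short.

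**Kaplan-Meier on the same data** (3,000 cohorts of 200). Median 10, Weibull, to 60 months: median 9.9 and upper quartile 17.0, against a plain 15.7. Median 16, Weibull, to 36 months: 16.0 and 27.2, against plain 13.2 and 19.5.

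**The case against.** The strongest reply is that Table 18-SEQ describes treatment details and serves no stated objective. The variable is openly defined as time to stop or end of observation, and as observed exposure its statistics are correct. On that view a footnote and a count of ongoing lines would be enough. This stands as far as weight goes: the primary endpoint is handled properly, and afatinib duration in this cohort is not affected because every patient has moved on to osimertinib. But the table calls the quantity treatment duration, carries no such footnote or count, and sits in a report that censors the same patients elsewhere.

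The size is assumption-driven, and that also stands. The worst cases have 36% to 39% ongoing, above the highest level in Protocol 9.5, and the 16-month anchor rests on subtracting medians from different populations. At the main 10% scenario of Protocol 9.5, the mean is 7% to 10% short. The optional second data collection in Protocol 9.7 would reduce this further, but it is not required.

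Other rules could pull the other way. SAP section 3 sets a missing stop date to the date of death for deceased patients, which can lengthen a line. Lines of unknown status, which are not modelled here, could be recorded too long if counted as not discontinued, or could drop out under the general missing-data rule in SAP section 4. These may offset part of the shortfall but do not correct it.

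Finally, SAP 4.2.7 has no visible content, and the sequencing tables after Table 22-SEQ are not shown, although the revision history names Table 27-SEQ. A Kaplan-Meier estimate for osimertinib alone may exist there. Table 18-SEQ as written would still need correction or a label.

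**Conclusion.** The concern holds. For confirmed ongoing lines the downward direction follows from the duration rule alone. Across the assumed range, the mean is 7% to 39% short and the upper quartile 7% to 37% short. The median is short by about 0.1 month if the true median is 10, and by about 3 months in the worst case with a true median of 16. The SD also shrinks. These sizes rest on the assumed medians, hazard shapes and follow-up windows, and on censoring independent of duration. The primary endpoint and overall survival are unaffected, so this is a change the plan should make to a descriptive table and not a threat to the main result.

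**What to change.** In Table 18-SEQ, replace the plain statistics with Kaplan-Meier quartiles and 95% CI counted from osimertinib start. Use the Table 20-SEQ event and censoring rules, including the rule for unknown status, and add a row with the numbers ended and censored. If the plain statistics are kept as well, label them as observed exposure to end of observation. Afatinib duration in Table 16-SEQ can stay as it is.

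The uncommon mutation cohort has the same duration rule in section 3. If Tables 21-UNC and 27-UNC use it (their text in SAP section 4 is not visible), treat them the same way with the line-level stop-date and ongoing fields, as in the rules for time to second-line treatment failure. The index-TKI rules of Table 36-UNC would not fit those tables.

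The cost is SAP wording, one extra row, and the existing Table 20-SEQ code with a different start date. No new data are needed. The downside is that the upper quartile may be reported as not reached: in 30% of simulated cohorts of 200 in the worst exponential case, 3% in the same case with a rising hazard, and none in the mildest case.
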